5.5. Exploratory Efficacy Endpoints

5.5.1. Time to Event Endpoints

Exploratory time to event endpoints include PFS, PFS on continued treatment, PFS2 and OS.

For each endpoint, quartiles (i.e., the 25th, 50th, and 75th percentile estimates) and the 2-sided 95% confidence intervals will be calculated from the Kaplan-Meier method. Survival probability and associated 95% CIs will be estimated at 6 months, 1 year, 18 months and 2 years as well. The number of events, number of participants censored, number of participants for each reason of censoring will be provided. The Kaplan-Meier plot of the survival distribution function will be presented with the number of participants at risk over time.

PFS

For PFS, participants who have no documented disease progression and death will be censored according to the rules in Table 3. For PFS-6 and DoR, similar censoring rules should be used if applicable.

Table 3 PFS and DoR censoring rules

Situation	Date of Censoring or Event	Outcome
No adequate tumor assessment at baseline or post-baseline and the participant has not died	Date of first dose of study treatment	Censored
No documented progression or death	Date of last adequate disease status assessment	Censored

Situation	Date of Censoring or Event	Outcome
Progression based on RECIST v1.1 with ≤ 1 missing consecutive scheduled tumor assessment before progression	Date of the earliest assessment that results in a finding of progression	Event
Death without documented progression with ≤ 1 missing consecutive scheduled tumor assessment before death	Date of death	Event
New anticancer therapy or procedure started prior to documented disease progression	Date of last adequate disease status assessment before the new therapy	Censored
Progression/Death after two or more missing scheduled tumor assessments	Date of last adequate disease status assessment before the missed assessments	Censored

Progression-free survival on continued nirogacestat treatment and PFS2

For the PFS analysis on continued nirogacestat treatment, only participants who continued the study treatment after the initial evidence of disease progression will be included. Participants who are alive and have not had a second progression will be censored at the last adequate disease status assessment date.

For PFS2, the second disease progression after participants discontinued the study treatment following the initial evidence of disease progression, and started the subsequent line of anticancer treatment, or death, whichever occurs first, will be considered as events for the PFS2 analysis. Participants who are alive and have not had a second progression on subsequent line of anticancer treatment will be censored at the last adequate disease status assessment date.

OS

For OS, in participants who have died, death will be considered an event and the death date will be used to calculate the time. For participants who are alive at the time of analysis, who are lost to follow-up or who withdraw consent for follow-up, the OS endpoint will be censored on the last date that participants were known to be alive or lost to follow-up.

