#### Standard of Care and Unmet Need

There are currently no Food and Drug Administration (FDA) approved therapies for OvGCT. Surgery, possibly with adjuvant chemotherapy, is the mainstay of initial treatment. Adjuvant

chemotherapy is typically with a platinum-based regimen: paclitaxel-carboplatin, cyclophosphamide-cisplatin, or bleomycin-etoposide-cisplatin. In the relapsed setting, which is the subject of this protocol, multiple chemotherapy regimens are used. These chemotherapy regimens are predominantly platinum based. After platinum, options are limited. One such example is bevacizumab. Bevacizumab used as single agent or in combination with chemotherapy (taxane or doxorubicin) in post-platinum recurrence has only modest activity ([Gershenson, Okamoto, and Ray-Coquard 2019](#)). A randomized trial in recurrent OvGCT evaluating paclitaxel (N=32) vs. paclitaxel + bevacizumab (N=28) showed only modestly improved activity with the combination of paclitaxel + bevacizumab. Paclitaxel monotherapy had an Objective Response Rate (ORR) of 25% (95% CI: 12-43%). Although the addition of bevacizumab increased the ORR to 44% (95% CI: 26-65%) no improvement in Progression Free Survival at 6 months (PFS-6) was seen. PFS-6 of paclitaxel + bevacizumab was 72% (95% CI: 57-89%) vs. PFS-6 of paclitaxel monotherapy of 71% (95% CI: 53-84%) in the trial ([Ray-Coquard et al. 2020](#)). Hormonal therapy (HT) has also been used in recurrent OvGCT and has shown some activity albeit inferior to that of paclitaxel. A retrospective analysis of HT ([Meurs et al. 2015](#)) showed an ORR of 18% with PFS and disease specific survival of 10 and 36 months respectively.

ORR from any monotherapy in the relapse setting is low. Furthermore, combination therapy in the relapse setting has failed to show an improvement in PFS rates. Therefore, there is an unmet need in this patient population for an agent with a higher response rate and the potential to improve PFS.

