  - b. Chest imaging: CXR or CT (contrast not required) required as described in the SoA and should be obtained per institutional standards.
  - c. EOT Visit: Scans only required if not performed within the last 6 weeks.
- 18. **Pre-Enrollment Review Form:** This form should be submitted at least 2 days prior to C1D1 in order to allow the Medical Monitor to review and approve eligibility prior to the participant being enrolled in the Interactive Response Technology IRT system (refer to the study reference manual for additional details)
- 19. **Enrollment:** Participants will be enrolled during the C1D1 visit, using the IRT system, only after all baseline assessments have been completed and participant has been confirmed to meet all eligibility criteria.
- 20. **Study treatment dispensing:** Participants will be dispensed study treatment using the IRT every cycle for the first year (C1-C13) and then every 3 cycles thereafter.
- 21. **Study treatment administration/Dosing Diary:** The first dose of study treatment (3 × 50 mg tablets) will be administered orally at the site at C1D1 followed by a 1-hour observation period. Following the first dose, participants will self-administer study treatment at 150 mg (3 × 50 mg tablets) twice daily (BID) (approximately every 12 hours, without regard to food) continuously in 28-day cycles throughout the study. Participants should record daily administration of each study treatment dose in the Dosing Diary. Refer to [Section 8](#) for more detail.
- 22. **AEs/AESIs/SAEs:** Will be monitored and documented from the time of informed consent up to 30 days after the last dose of study treatment. Participants reporting AEs/AESIs/SAEs of reproductive system disorders will have hormone levels assessed every 3 months until event resolution (or for at least 90 days after discontinuing study treatment).
- 23. **Every 3 Cycles and On:** Following C13D1 participants will return every 3 cycles for study visits until end of study participation.
- 24. **Remote Monthly Wellness Checks:** Monthly (every 28 days [+/- 2 days]) telephone or email contact is required following C13D1 until EOT. The wellness checks may be replaced by a face-to-face interaction when study visits occur, provided the wellness information can be obtained during the visit. Refer to [Section 11.2.7](#) for more detail.

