## 9. DISCONTINUATION OF STUDY TREATMENT AND PARTICIPANT DISCONTINUATION/WITHDRAWAL

It may be necessary for a participant to permanently discontinue study treatment (nirogacestat) early. In this case, the participant will return to the site for an EOT visit and a post dose safety

follow-up (FUP) visit (refer to SoA; [Section 1.3](#) for a complete list of required assessments to be conducted).

Reasons for discontinuation of study treatment at any time may include:

- Clinical (including physical examination) or radiographic (using RECIST v1.1) evidence of progressive disease (PD);
  - Treatment after Initial Evidence of Disease Progression
    - Study treatment may be continued at the investigator's discretion if the participant is clinically stable as defined by the following criteria:
      - Absence of clinical signs and symptoms of disease progression
      - No decline in ECOG performance status
      - Absence of progressive tumor at critical anatomical sites (e.g., cord compression) requiring urgent alternative medical intervention.
    - The participant will be reassessed at the next protocol-defined CT or MRI scan for tumor measurement in order to rule out pseudo-progression.
      - If repeat imaging demonstrates CR, PR, or SD compared to the first scan that showed disease progression, treatment with study treatment may be continued.
      - If repeat imaging demonstrates PD, defined as  $\geq 10\%$  increase in tumor burden compared to the first scan that showed disease progression, participants should be discontinued from study treatment.
    - All decisions to continue study treatment beyond initial progression must be discussed with the Medical Monitors and documented in source documents.
  - Adverse events requiring removal from protocol therapy as stated in [Section 9.1](#). Any SAE (refer to [Appendix A5-1.3](#) for SAE criteria), clinically significant AE (refer to QTcF stopping criteria, [Section 9.1.2](#)), severe laboratory abnormality (refer to liver chemistry stopping criteria, [Section 9.1.1](#)), any grade  $\geq 3$  hypersensitivity reaction, anaphylaxis, intercurrent illness, or other medical condition which indicates to the Investigator that continued participation is not in the best interest of the participant;
  - The initiation of emergent treatment (e.g., radiotherapy, surgery, or systemic therapy including chemotherapy, small molecule inhibitors, immunotherapy, or targeted therapy) for granulosa cell tumor;

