### Evaluation of best overall response

The best overall response is the best response recorded from the start of the study treatment until disease progression/recurrence (taking as reference for PD the smallest measurements recorded since the start of study treatment). The participant's best response assignment will depend on the achievement of both measurement and confirmation criteria (defined below).

Target Lesions	Nontarget Lesions	New Lesions	Overall Response
CR	CR	No	CR
CR	Non-CR/non-PD	No	PR
CR	Not evaluated	No	PR
PR	Non-PD or not all evaluated	No	PR
SD	Non-PD or not all evaluated	No	SD
Not all evaluated	Non-PD	No	NE
PD	Any	Yes or No	PD
Any	PD	Yes or No	PD
Any	Any	Yes	PD

CR=Complete Response; NE=Not Evaluable; PD=Progressive Disease; PR=Partial Response; SD=Stable Disease.

Participants with a global deterioration of health status requiring discontinuation of study treatment without objective evidence of disease progression at that time will be classified as

having “symptomatic deterioration”. Every effort should be made to document the objective progression even after discontinuation of treatment.

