5.4.1. PFS-6

PFS-6 will be estimated using Kaplan-Meier method and 2-sided 95% CI based on log-log transformation. Participants who do not progress or die will be censored according to the censoring rules for the PFS as outlined in Table 3.

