5.4.4. Duration of Response (DoR)

DoR will be summarized with standard summary statistics and will also be analyzed using the Kaplan-Meier method for confirmed responders only. Quartiles (i.e., the 25th, 50th, and 75th percentile estimates) and the 2-sided 95% confidence intervals will be presented. If progression

or death was not observed, the participant will be censored according to the censoring rule for PFS (see Table 3). If there are censored participants in DoR, time to censoring will be used to summarize the range. The Kaplan-Meier plot will be provided.

By-participant listing will be provided for responders. The listing will include number of completed cycles before first response, date of first response, date of first disease progression or death if any, censored or event will be marked.

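### PFS-6 and DoR censor failures without RECIST progression, and no sensitivity analysis shows how far the estimates depend on that rule

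*SAP*

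**What the plan says.** SAP 5.4.1 estimates PFS-6 by Kaplan-Meier and states: "Participants who do not progress or die will be censored according to the censoring rules for the PFS as outlined in Table 3". SAP 5.4.4 carries the same rule to DoR: if progression "or death was not observed, the participant will be censored according to the censoring rule for PFS (see Table 3"). SAP 5.5.1 repeats the link: "For PFS-6 and DoR, similar censoring rules should be used if applicable".

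In Table 3, only progression by RECIST v1.1 or death can be an event. Three rows matter here:

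- The situation "New anticancer therapy or procedure started prior to documented disease progression" is censored at the last adequate assessment preceding that therapy.
- A participant with neither progression nor death on record is censored at the last adequate assessment.
- Progression or death after two or more missed scheduled assessments is censored at the last adequate assessment before the gap.

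The protocol foresees failure without RECIST progression. Section 9 opens its list of reasons for stopping treatment with "Clinical (including physical examination) or radiographic (using RECIST v1.1) evidence of progressive disease (PD"). Appendix 3 names symptomatic deterioration as a category for participants who must stop without objective progression, and adds: "Every effort should be made to document the objective progression even after discontinuation of treatment".

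The Schedule of Assessments has tumour imaging up to EOT and none at the safety follow-up or the 2-year check-in. For the EOT visit, footnote 17c says: "Scans only required if not performed within the last 6 weeks". Protocol 11.1.1 permits, but does not require, unscheduled scans when progression is suspected.

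SAP 5.5.1 will report the number censored for each reason. The only sensitivity-analysis section, 5.3.2, concerns ORR and plans none. Nothing equivalent exists for PFS, PFS-6 or DoR.

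**The concern.** Kaplan-Meier treats a censored participant as having the same outlook as those still at risk. That is doubtful for someone who stops because the disease is clinically worse, or who is switched to another drug before a scan meets the RECIST threshold. Removing such participants from the risk set, rather than counting them as failures, pushes PFS-6 up. Among confirmed responders it lengthens DoR in the same way.

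With no comparator arm, any such bias goes straight into the reported figure. The trial is open-label with local reading, and the investigator decides when to stop or switch. The protocol synopsis quotes PFS-6 of 71% and 72% for the two arms of the randomised paclitaxel trial as background, so a shift of a few points could change how the result is read.

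Protocol 12.3 says the SAP will set out how intercurrent events affecting the endpoints are handled. For clinical progression without RECIST progression it gives only the default row of Table 3.

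**Working it through.** **No plan figure to reproduce.** The documents state no target, power or precision for PFS-6 or DoR. The check is therefore an illustration of the rule at work.

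**Inputs**
- N = 53, the number enrolled (SAP 5.8), taken as all treated.
- Scans at weeks 8, 16 and 24 (C3D1, C5D1, C7D1; SAP 1.3). C7D1 is Day 169. Six months under SAP 4.1 is 6 × 30.4375 = 182.6 days, so all three scans fall before it.
- True failures by 6 months: 15 (assumption). This gives PFS-6 = 38/53 = 71.7%, close to the cited 71–72%.
- Number of the 15 who stop or switch without RECIST progression: 0, 3 or 6 (assumption; the documents give no figure).
- True failures are spread evenly over the three intervals, with no other censoring.

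**Formula.** A participant who fails without RECIST progression is censored no later than an EOT scan, so leaves the risk set before the next scheduled scan. With c censored and e RECIST events per interval, S(6 months) is the product over the three scans of (1 − e/n), where n is the number at risk after removing earlier events and all censored participants so far.

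**Results**
- 0 of 15 censored (c = 0, e = 5): 48/53 × 43/48 × 38/43 = 38/53 = **71.7%**.
- 3 of 15 censored (c = 1, e = 4): 48/52 × 43/47 × 38/42 = **76.4%**, or +4.7 points.
- 6 of 15 censored (c = 2, e = 3): 48/51 × 43/46 × 38/41 = **81.5%**, or +9.8 points.

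**Timing.** With 6 censored, all in the first interval: 44/47 × 41/44 × 38/41 = 80.9%. All in the third: 50/53 × 47/50 × 38/41 = 82.2%. Timing matters little.

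**Range.** The same formula, with the share of true failures censored under Table 3 running from 10% to 50%:

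| True PFS-6 | Bias at 10% | Bias at 50% |
|---|---|---|
| 60% | +2.9 points | +16.6 points |
| 71% | +2.3 points | +12.8 points |
| 80% | +1.7 points | +9.3 points |

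The biases are the same for N = 43, because only proportions enter. At a share of zero there is no bias.

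**DoR.** The mechanism is the same, but the documents give no DoR figure, so its size was not computed.

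**Do the planned outputs reveal this?** A participant stopped for clinical progression who has not started new therapy falls in the same Table 3 row as one who is on treatment and progression-free, so the count by censoring reason merges them. SAP 5.1 has a single disease-progression reason for stopping treatment, not split into clinical and radiographic. Neither count is tied to 6 months.

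**The case against.** The strongest reply is that Table 3 is a conventional rule and that safeguards exist. Participants who complete EOT have either a scan from the previous 6 weeks or a new one. Unscheduled scans are allowed whenever progression is suspected, and Appendix 3 asks sites to document progression after discontinuation. Someone who stops clinically and has not switched can still become an event if RECIST progression or death is recorded later. Counts by censoring reason, numbers at risk and discontinuation reasons are all planned. The endpoints are descriptive, with no hypothesis test.

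Most of this stands. It means the rule should remain primary, and that a reader who infers that no scans can follow EOT goes too far: none are scheduled. It reduces the problem without removing it. The request to document progression has no visit behind it. Later progression does not rescue a participant who has already started new therapy. Table 3 also does not say how its missed-assessment condition works after EOT, when no assessment is scheduled.

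A reader might also infer that PFS-6 is certainly biased upward. The documents do not support that. The number of such participants is unknown, and stops for other reasons, such as an adverse event, need not be informative. If stops were unrelated to prognosis, the planned estimate would remain valid for RECIST-defined PFS-6. Counting those stops as failures would then describe a different, composite endpoint and would not reveal a bias.

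Nor do the documents rank PFS-6 as the main secondary endpoint. The stated PFS comparison is with bevacizumab monotherapy (median 9.3 months), and the 71–72% is background.

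**Conclusion.** The concern holds conditionally. If participants stop or switch because they are doing badly and have no documented RECIST progression, Table 3 censors them, and PFS-6 and DoR are likely to be too high. The plan contains nothing that shows by how much.

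In the illustration, 3 to 6 such participants among 53 move PFS-6 by about 5 to 10 points. That rests on assumed counts, on all of those participants being true failures by 6 months, and on no other censoring. With none, the effect is zero. This is a gap in reporting that is cheap to close. It is not an error in the primary rule.

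**What to change.** Keep Table 3 as the primary rule. Add one pre-specified Kaplan-Meier sensitivity analysis for PFS, PFS-6 and DoR that counts as events:

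- discontinuation for disease progression or symptomatic deterioration without RECIST progression, at the discontinuation date;
- start of new anticancer therapy, at its start date;
- progression or death after two or more missed assessments, at its actual date.

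Split the already planned counts by censoring reason at 6 months, and state in Table 3 where symptomatic deterioration falls.

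Much of the data is already planned. Clinical stops can be found by checking the disease-progression discontinuation reason (SAP 5.1) against the RECIST assessments, and subsequent therapy is recorded under Protocol 11.2.8. The documents define no separate date for clinical progression, which is why the discontinuation date is used. SAP 5.1 has no category for symptomatic deterioration, so the SAP should say which reason captures it.

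The cost is one extra analysis and a less favourable figure beside the primary one. That figure should be presented as the pessimistic end, because some switches or stops may not reflect progression.

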5.5.2. Next Generation Sequencing status

The NGS status will be assessed at baseline to detect FOXL2 C134W mutation as well as other genomic alterations and correlate these with response. A 2×2 table will be generated for FOXL2 C134W mutation (yes/no) vs. Objective Response (yes/no) to evaluate the correlation between mutation and ORR with the Spearman rank correlation and its 95% CI provided. Within each status, the percentage of participants with objective response (CR + PR) and its 2-sided exact 95% CI based on the Clopper-Pearson method will be provided. The response ratio of participants with alteration vs. those without alteration and its 95% CI will also be provided using the Farrington-Manning method.

NGS status data will be listed. Correlation between ORR and other genomic alterations will be analyzed post hoc if deemed necessary.

5.5.3. Inhibin A&B, Follicle-stimulating Hormone, Estradiol, CA-125, and AMH/Mullerian Inhibiting Substance (MIS)

Tumor and hormonal markers Inhibin A, Inhibin B, AMH/MIS, follicle-stimulating hormone, estradiol, and CA-125 will be assessed per the SoA (see Table 2 in the protocol). Summary statistics and change from baseline at each visit will be provided. Box and whisker plots displaying the values over time by nominal visit will also be provided.

To evaluate association between changes in tumor size over time with FSH and estradiol level, a figure with the percent change from baseline in tumor size on one y-axis and the change from baseline in FSH and estradiol level on a secondary y-axis over time (x-axis) will be generated.

5.5.4. Time to Response

Time to first objective response will be calculated as time in months from first dose until date of the first documented response (CR or PR). Only participants with confirmed response will be included and the time in months to first response will be summarized with standard summary statistics.

5.6. Safety Analyses

Safety analyses will be conducted using the Safety Analysis Set.

5.6.1. Study Drug Exposure and Compliance

Extent of exposure will be summarized as follows:

- Duration of exposure in months (last dose of study treatment date – first dose date + 1 /30.4375) summarized as a continuous variable
- If a data cut-off date is used and some participants are receiving treatment at the time of analysis, the last dose date at the time of the data cut-off for analysis will be the data cut-off date
- Number and percentage of participants who received treatment with a duration of at least 1 cycle (28 days), 2 cycles, 3 cycles, 4 cycles, 5 cycles, 6 to 12 cycles, 13 to 25 cycles and 26 cycles or longer
- Actual dose intensity (mg/day) – calculated as the cumulative dose received / duration of exposure in days
- Relative dose intensity (%) defined as $100 \times (\text{total cumulative dose received}) / (\text{planned cumulative dose, where planned cumulative dose is } 300 \text{ mg/day multiplied by duration of exposure in days})$ and summarized as a continuous variable
- Number and percentage of participants with a dose modification (dose reduction and/or dose interruption as reported on eCRF) as well as reasons for dose modification
- Number and percentage of participants with a dose reduction (as reported on eCRF)
- Time (in days) to the first dose reduction and first dose interruption will be summarized as continuous variables
- Number and percentage of participants with a dose interruption including the number of days interrupted
- Number and percentage of participants with study treatment discontinued
- Special Situations in exposure are defined as Abuse, Misuse, Occupational Exposure (inadvertent/accidental), or Medication Error of study treatment. The number and percentage of participants with each and overall special situations resulting in an adverse event will also be summarized.

A by-participant listing will be presented for exposure to study treatment and dosing modifications.

